As Vapotherm Hi-VNI technology becomes more common-place in hospital standard of care & practice, HVNI therapy may also have a demonstrable effect on improving patient ambulation and mobility. Mobility represents a key factor in the timely improvement of patient health, and in end-of-life cases it can have a mental impact⁸. In addition to the patient benefits, ambulation and early ambulation & mobility can also reduce the patient hospital resource allocation and reduce the length of stay (LOS). Some hospitals have included patient ambulation metrics as a key success factor, and this also can play a role to stepping-down

Vapotherm, Inc

HVNI Ambulation Feasibility Study

Confidential

the patients to less critical care environments. The goal of this study is to establish a low risk model, modified from the 6MWT, for patients with dyspnea: (1) evaluate the effect of HVNI on ambulation, and (2) assess the impact HVNI use may have on improved outcomes when compared to standard TAU (HVNI).

Vapotherm, Inc
HVNI Ambulation Feasibility Study
Confidential

II. Overall Study Objective

The **overall objective** of this study is to evaluate the ability of HVNI to improve patient ambulation relative to a treatment as usual (TAU).

The **hypothesis** is that HVNI therapy, when implemented in conjunction to ambulatory practices, will be more effective than TAU to improve patient mobility by reducing the patient's perceived dyspnea and exertion via maintaining oxygenation (reduced desaturation) and supporting ventilation (reduced work of breathing [WOB]).

To test this hypothesis, the study will be conducted with the following specific aims:

Aim #1: Primary Outcome. The primary endpoint is exercise performance, defined as the distance and duration of patient ambulation.

Aim #2: Secondary Outcomes. The secondary endpoints evaluate the patient recovery interval, defined as the recovery time (return time to baseline perceived dyspnea). Other endpoints will include: vital signs (heart rate [HR], respiratory rate [RR], blood pressure [BP]), arterial oxygen saturation (SpO₂), rated perceived exertion (RPE), and rated perceived dyspnea (RPD).

Aim #3: Tertiary Outcomes. The tertiary endpoints evaluate the clinician perception scores. For the clinician perceptions this will include: technical/clinical difficulties, patient comfort & tolerance, ease of use, monitoring & support for therapy, and expected/perceived patient outcomes.

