Subjects will be solicited by research staff and consented prior to participation in this feasibility study (Aims 1-3). Once consented, the participants will complete all Aims during the course of participation in the study, per the TAU at each site. Compensation will be provided to participants for enrollment into this study.

Sample Size:

To provide a sample data set, we will enroll up to 32 subjects to complete this feasibility assessment, with a calculated sample size of N=26 plus a 20% failure rate. This will provide sufficient initial data to inform the appropriate sample size of a follow-on randomized study.

This sample size was calculated through use of references that approximated similar studies ^{1,32}. McCarthy et al. found a mean difference of 42.93m with 95CI: 32.64 – 55.21m when evaluating patient ambulation with and without adjunctive therapy ³². For this study, using a desired power of 90% with alpha=0.05, the sample size is estimated at 26 to show a difference in data between the control and test groups.

Vapotherm, Inc
HVNI Ambulation Feasibility Study
Confidential

VI. Study Procedures

This feasibility study is non-blinded by necessity, since the provided therapies have different devices. No randomization will be incorporated into this feasibility study design. The study arms will be performed as a crossover design, baseline performed first followed by the test period. Study model for the ambulation test is a modified 6-minute walk test. Figure 1 illustrates an overview of the study procedures. This feasibility study will evaluate the baseline, performance, recovery, and clinical assessment indices to demonstrate the effect between TAU and HVNI during ambulatory practice.

Screening, Enrollment, & Management

Upon screening, subjects will be asked to participate in this study, and if so they will be consented prior to enrollment. Subjects are instructed that if at any time during the study they are free to stop the test and discontinue study participation. All study procedures will be explained to the subject.

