Baseline Characterization Sitting down, the subject will be setup and prepared for the ambulation test with appropriate data recording devices and supplemental oxygen (not HVNI). The subject will be allowed to acclimate to the supplemental oxygen during this period of time. While subject is at rest, standing up, the following data will be collected (see Table 1): RR, HR, BP, SpO₂, and RPD (Modified Borg scale 0-10). For the RPD & RPE, the coordinator will record patient scores, the FiO₂ and flow settings for any supplemental oxygen provided to the patient before/during/after this baseline phase. TAU will not include HVNI in this study period. The Ambulation Test will be performed after the baseline characterization is. The definition for this ambulation test will be to walk until 18 minutes has elapsed or the patient is unable to continue. A timer will keep track of the test duration, and the clinician will keep track of the distance traveled during ambulation. At test start, test end, & 1-minute intervals the subjects will be asked to rate their RPE (Modified Borg scale 0-10). The subject vitals will be monitored during this ambulation test and recorded as follows: HR, RR, SpO₂. The ambulation test will end if the subject has completed 18 minutes, stops walking for more than 10 seconds, has to sit down, has any adverse events, or should the investigator deem necessary.

Recovery Interval will begin immediately following the end of the Ambulation Test. The subject will perform this recovery interval while safely seated. The time to return to the subject's resting-while-standing RPD score (Baseline) will be used as recovery time. At the end of the recovery interval, record the subject RR, HR, BP, SpO₂, and RPD & RPE. Any adverse events will be recorded. Any exacerbations from ambulation walk test will be recorded during the recovery interval. Record the recovery end time and date.

After the Recovery Interval is complete, all associated data will be collected including clinician perception/satisfaction scores. Then the study will pause until the next ambulation test is scheduled. The next ambulation test will be determined per standard practice and when deemed appropriate by the investigator.

Test Session

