All other pharmaceutical and medical treatment will remain the purview of the attending physician and will be administered per the current standards. This study is designed to evaluate only intervention of HVNI in conjunction with standard (TAU) ambulatory practice, and it is assumed that the ancillary interventions will

Vapotherm, Inc
HVNI Ambulation Feasibility Study
Confidential

follow common clinical practice guidelines and conventions. All treatments given to the subjects will be noted on their CRFs.

VapoTherm, Inc
HVNI Ambulation Feasibility Study
Confidential

VII. Data Collection

Table 1. Key study data and collection points.

	Baseline Characterization	Ambulation Test	Recovery Interval	@ Study End
Patient History & Health	X			X
Treatment: Flow & O2	X	X	X	X
Physiologic Parameters	X	X	X	X
Performance Parameters		X		
Recovery Parameters			X	
Clinician Perception Scores			X	X
Disposition	X			X

Patient enrollment data collection will include patient history, health, demographics, and interventions. For each test session the following data will be recorded for comparison.

Physiologic Parameters

- SpO₂, HR, RR, BP, RPE, RPD

Performance Parameters

- Test duration and test distance traveled

Recovery Parameters

- Return time to baseline RPD, HR, RR, BP, SpO₂, RPD, RPE

Primary Endpoint

- Distance and duration of exercise during ambulation

Secondary Endpoints

- Physiologic parameters – SpO₂, HR, RR, BP, RPE, RPD
- Recovery parameters: return time to baseline Rated Perceived Dyspnea score
- Modified Borg scale scores – Rated Perceived Exertion (RPE), Rated Perceived Dyspnea (RPD)

Tertiary Endpoints

- Clinician perception of patient respiratory response to therapy, ranging from NO Response to Excellent Response, as continuous VAS.
- Clinician perception of frequency of rain-out, interface slippage or other technical/clinical difficulties applying therapy, ranging from Never to Frequent as continuous VAS.
- Clinician perception of patient comfort and tolerance of therapy, ranging from Very Poorly Tolerated to Very Well Tolerated as continuous VAS.

Vapotherm, Inc

HVNI Ambulation Feasibility Study

Confidential

- Clinician perception of Simplicity of set-up and use, ranging from Complex to Setup and Use to Simple to Setup and Use, as continuous VAS.
- Clinician perception of Monitoring and support of therapy required (adjustments, refilling fluids, adjusting interface), ranging from Almost Constantly to Almost Never, as continuous VAS.

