VIII. Statistical Analysis

The data analysis will be “per protocol.” Baseline patient demographics and characteristics will be summarized, and appropriate statistical testing will be performed for the continuous and categorical variables. Assuming a non-normal data distribution for this crossover study design, the non-parametric Wilcoxon Signed Rank Sum test will be performed with significance interval of 0.05 on all applicable variables. Otherwise, for the categorical variables, the Fisher’s Exact test will be performed. Data will be compared and graphed accordingly for a visual comparison with accompanied statistical notations.

IX. Risks and Discomforts

This pilot study does not present significant risk to patients, as supplemental oxygen is routinely provided to patients and the 6MWT is a standard/routine practice³³. The Treatment-as-Usual at the study sites involves the application of simple supplemental oxygen during mobilization. Use of the high flow nasal cannula therapy has no known risks and has been used in the clinical setting for approximately seventeen years without known reports of adverse events related to the administration of high nasal flows when appropriately conditioned to near body temperature and fully humidified. The literature indicates that approximately only 4 cmH₂O of distending pressure may be generated in the upper airway^{34,35} which is well below any known threshold for injury. In addition, it has been demonstrated that delivery of high flows of conditioned gas from a nasal cannula has a positive effect on airway mucosal function^{36,37}. The patients will be closely monitored as part of standard medical practice. Ambulation is implemented as part of the standard care practice for the patients included in this study.

For these reasons, we have determined that this study represents non-significant risk to the subjects, beyond the discomfort related to routine ambulation therapy.

X. Potential Benefits

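### The primary endpoint is two measures, each tested at 0.05, but the sample size covers distance at most and no rule says how a split result is read

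*Combined protocol and SAP*

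**What the plan says.** - **Endpoint.** Section II, Aim #1: "The primary endpoint is exercise performance, defined as the distance and duration of patient ambulation". Section VII, Primary Endpoint, repeats it: "Distance and duration of exercise during ambulation".
- **Recording.** The two are separate quantities. Section VII, Performance Parameters, lists "Test duration and test distance traveled", and section VI (Control Session, Ambulation Test) says "A timer will keep track of the test duration, and the clinician will keep track of the distance traveled during ambulation". No combined score is defined.
- **End of the walk.** Section VI gives the stopping conditions, beginning "The ambulation test will end if the subject has completed 18 minutes, stops walking for more than 10 seconds".
- **Analysis.** Section VIII: "the non-parametric Wilcoxon Signed Rank Sum test will be performed with significance interval of 0.05 on all applicable variables".
- **Sizing.** Section V, Sample Size: "using a desired power of 90% with alpha=0.05, the sample size is estimated at 26 to show a difference in data". The only planning effect given there is 42.93 m, with a 95% interval of 32.64 to 55.21 m, from a cited review. No effect in units of time is given.
- **Hypothesis.** Section II says that HVNI "will be more effective than TAU to improve patient mobility".

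No section gives a hierarchy, a split of alpha, or a statement of whether both measures, either one, or a named one decides the primary result.

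**The concern.** Read as written, one primary endpoint gets two tests at 0.05, while the power statement rests on an effect in metres and does not mention duration.

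The two measures can disagree. Distance is pace multiplied by time, so a subject may walk longer but slower. A subject who reaches 18 minutes in both sessions has a duration difference of exactly zero, while the distances can still differ.

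If one test is significant and the other is not, the same data support reporting the primary endpoint as met or as not met. The study is unblinded, so that choice could be made with the results in view. The study is also meant to inform the size of a follow-on randomised trial. With no lead measure named, that sizing could rest on whichever measure looked better. If the two tests agree, nothing changes.

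**Working it through.** **1. The plan's own figure.** For paired differences, n = ((z_alpha + z_power) × SD / difference)². The protocol gives the difference (42.93 m), alpha (0.05, sidedness not stated) and power (90%), but no SD, so N=26 can be neither reproduced nor refuted. Solving backwards, two-sided:

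SD = 42.93 × √26 / (1.960 + 1.282) = 67.5 m (64.9 m with the t distribution).

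Neither SD is in the documents. Enrolment does reproduce: 26 × 1.2 = 31.2, rounded up to 32.

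**2. Assumptions for the rest.** None of these is in the documents:
- each measure has 90% power on its own, two-sided at 0.05, with 26 completers (the reading kindest to the plan);
- the standardised effects are equal;
- the paired differences are bivariate normal without ties;
- the correlation between the two differences is varied from 0 to 0.95.

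No SD in metres is needed.

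**3. Closed form at correlation 0.**
- Either measure counts, no true effect: 1 − 0.95² = 0.0975.
- Both required, both effects real: 0.90² = 0.81.
- Exactly one significant, both effects real: 2 × 0.90 × 0.10 = 0.18.

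**4. Across correlations.** Simulation of the planned test: exact two-sided Wilcoxon signed-rank, 26 pairs, critical value 98, standardised difference 0.68, 200,000 runs per setting. The bivariate normal approximation is in parentheses; its split figure is the power for at least one minus the power for both.

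| Correlation | Error if either counts | Power if both required | Split result, both effects real |
|---|---|---|---|
| 0 | 9.8% (9.75%) | 81.5% (81.0%) | 17.6% (18.0%) |
| 0.5 | 9.1% (9.1%) | 83.3% (83.2%) | 13.8% (13.5%) |
| 0.8 | 7.9% (7.8%) | 85.7% (85.6%) | 9.2% (8.8%) |
| 0.9 | 7.1% (7.0%) | 86.9% (86.9%) | 6.7% (6.2%) |
| 0.95 | 6.7% (6.5%) | 87.9% (87.8%) | 4.9% (4.4%) |

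If both are required, the error rate stays at or below 5%. At correlation 1 the problem disappears.

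**5. If more subjects complete.** Both-required power is 87% / 89% / 91% at 29 completers and 91% / 93% / 94% at 32, for correlations 0 / 0.8 / 0.95. With the planned 20% failure rate, 32 × 0.8 = 25.6, so about 26 completers is what the plan itself expects.

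**6. If alpha is split.** At 0.025 each, power per measure with 26 completers is Φ(3.242 − 2.241) = 0.84, or 0.83 with the t distribution. Reaching 90% per measure needs 31 completers.

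**The case against.** Several counter-arguments have force.

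- **The sizing is coherent for distance alone.** The only planning effect is in metres, so the natural reading is that the 90% and 0.05 refer to distance. This stands. A reader might infer that N=26 is wrong or that the study is underpowered, and the documents do not support that: without an SD the figure cannot be checked. What is missing is the role of duration.
- **The inflated error rate needs an either-one rule.** A reader might infer that the plan runs at nearly 10% error. No section states such a rule, and joining the two measures with *and* leans towards requiring both, in which case error stays at or below 5% and only power is affected. This weakens the error half of the concern. It does not settle the matter, because *and* may only list components.
- **Zero correlation is implausible.** Both measures come from the same walk, so 0.8 to 0.95 is the more sensible range and the values at 0 are outer limits. That is a judgement; the protocol gives no correlation.
- **The shortfall under a both-required rule goes away if all 32 complete.** True (91-94%), but the plan assumes 20% failures.
- **The simulation omits the cap on duration.** It has no ties and assumes equal effects, so the percentages are illustrative. Ties or a weaker effect on duration could make splits more frequent.
- **This is a feasibility study.** It is non-randomised, in fixed order and unblinded, so a p-value cannot separate HVNI from period or practice effects, and no stated decision hangs on the primary result. This limits the consequence. It does not remove the point, because the protocol chose a directional hypothesis, a formal power statement and significance tests.

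**Conclusion.** The concern holds in this form: two separately recorded measures make up the primary endpoint, each is tested at 0.05, the one power statement covers distance at most, and nothing says how a split result is read. That omission is certain from the text.

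Its numerical size is not. Under the assumptions listed and a correlation of 0.8 to 0.95, the departures are a few percentage points: about 6.5-8% error instead of 5% if either measure counts, or about 86-88% power instead of 90% if both are required. About one trial in eleven to one in twenty would split when both effects are real. The limits at correlation 0 are 9.8%, 81% and 18%.

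The practical consequence is modest given the design. The repair is nearly free and should be made.

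**What to change.** Before data are analysed:

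1. In the Primary Endpoint and Statistical Analysis sections, state that distance is the primary measure, tested at 0.05, and that duration is secondary. Alternatively, test duration at 0.05 only if distance is significant, and otherwise report it descriptively.
2. In the Sample Size section, state that N=26 and 90% power refer to distance.

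Distance is suggested because the only planning effect is in metres. Alpha stays at 0.05 and N at 26.

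If the sponsor wants both measures to count, state the rule and restate the power under the same assumptions: about 81-88% at 26 completers if both are required (correlation 0 to 0.95), or about 83% per measure if either counts at 0.025 each.

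The cost is a few sentences, with no added subjects, visits or data. The price is that a result on duration alone could no longer be called a primary success.

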These **endpoints** will establish the effect HVNI therapy may have on improving patient ambulation relative to TAU, while potentially demonstrating the effect of HVNI on hospital resource allocation and patient comfort.

Vapotherm, Inc

HVNI Ambulation Feasibility Study

Confidential

III. Subject Selection

Subjects will be identified and recruited by study investigators. The feasibility study will take place at a clinical setting (e.g. hospital, academic center, out-patient facility), where testing can be performed with appropriate supervision and staff training to maintain patient safety. The test model is a modified 6MWT. Initial contact will be made by the study investigators, and the participants may or may not decide to enroll. Compensation will be provided to participants for enrollment into this study.

Inclusion Criteria

1. Adults over the age of 18 years
2. Demonstrated respiratory distress upon mild to moderate exertion (e.g. dyspnea upon standing, walking, etc.)
3. Candidate for clinical ambulation/mobilization
4. GOLD 4 spirometry or GOLD 3 with significant dyspnea on exertion with or without supplemental oxygen

Exclusion Criteria

1. Hypoxemia at resting baseline with $SpO_2 < 88\%$ with supplemental oxygen
2. Inability to provide informed consent
3. Pregnancy
4. Known contraindication to perform ambulation, per site SOC practices
5. Inadequate respiratory drive or any known contraindications to HVNI
6. Inability to use nasal cannula and HVNI therapy
7. Agitation or uncooperativeness
8. Determined by the attending clinician to be sufficiently unstable or unsuitable for this feasibility study

IV. Study Design

The study objective is to evaluate the ability of HVNI to improve patient ambulation relative to TAU by using a modified 6MWT model. The hypothesis is that HVNI therapy, when implemented in conjunction to ambulatory practices, will be more effective than TAU to improve patient by reducing the patient's perceived dyspnea and exertion via maintaining oxygenation (reduced desaturation) and supporting ventilation (reduced WOB).

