This will be a feasibility study, performed as a prospective, crossover trial to evaluate the potential patient improvement during ambulation while on HVNI relative to TAU. Patients who fit the criteria for inclusion will perform ambulation for each study period: the baseline period (TAU) followed by the test period (HVNI). The clinical management will otherwise remain unchanged based on the site SOC practices. The patient FiO_2 and flow values will be recorded while on any supplemental oxygen. Subjects will wear appropriate gear and, when applicable, have mobile carts to provide supplemental oxygen therapy (e.g. HVNI VTU) during ambulation.

This feasibility study design focuses on three distinct phases: (1) baseline characterization, (2) performance measures of ambulation, and (3) clinician perceived satisfaction scores. The baseline characterization is to provide patient background, history, and initial relevant clinical evaluation from Aim 2. Performance

Vapotherm, Inc

HVNI Ambulation Feasibility Study

Confidential

measures from Aims 1 & 2 will provide physiologic relevant indices before/during/after ambulation session and will be used for meaningful comparison between study arms. Lastly, Aim 3 will provide an overall assessment from the clinician perceived satisfaction scores.

This feasibility study will involve two study periods: baseline (TAU) and test (HVNI). Baseline period will be administered first, followed by the test period. Patients deemed in need of ambulation (per inclusion/exclusion criteria) will be enrolled into the study and will complete both study periods:

1. Treatment as usual (TAU) of standard practices (control arm) for ambulation at site
2. Vapotherm HVNI therapy (test arm) administered as described below during ambulation at site

This feasibility study will be conducted in a research facility and where testing can be performed with appropriate supervision and staff training to maintain patient safety. This current study uses a modified 6MWT ambulation test to evaluate the patient performance. Primary and secondary outcomes will be completed upon the completion of each study arm's ambulation test. Tertiary outcomes will be completed upon study. All respiratory interventions will be tracked during the study window, and disposition and mortality will be tracked for each patient.

V. Subject Enrollment

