Upon enrollment, appropriate study data will be collected (see below under Data Collection), including patient demographics, anthropometrics, and applicable history (LTOT user, positive-airway pressure therapy user, current respiratory therapy). Subjects will be managed by routine care while study data is captured as shown in the timeline below (Table 1). All decision making for patient ability to ambulate and continue study procedures will be made per standard practice at the site, using the judgment of the research team.

[figure not shown]

Figure 1. Framework of the clinical study procedures discussed within this protocol.

Vapotherm, Inc

HVNI Ambulation Feasibility Study

Confidential

Control Session

The Control session is treatment as usual (TAU), without use of HVNI during any time of this study period.

The Control session will follow three phases (see Figure 1 & Table 1): Baseline Characterization, Ambulation Test, and Recovery Interval. After these phases are complete, the next ambulation exercise will be determined per standard practice and when deemed appropriate by investigator.

Prior to the Control Session baseline characterization, the subjects should wear comfortable clothing, appropriate walking shoes, and usual walking aids (cane, walker, etc.). No vigorous exercise should be performed 2 hours prior to the ambulation test³³.

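### Every subject walks on TAU first and HVNI second, so the planned paired test cannot separate an HVNI effect from an order effect

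*Combined protocol and SAP*

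**What the plan says.** The order is fixed in two places. IV. Study Design: "Baseline period will be administered first, followed by the test period". VI. Study Procedures: "The study arms will be performed as a crossover design, baseline performed first followed by the test period", and "No randomization will be incorporated into this feasibility study design". All subjects complete both sessions, and no HVNI-then-TAU sequence is described.

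The gap between the two walks has no set length (VI, Control Session): "The next ambulation test will be determined per standard practice and when deemed appropriate by the investigator". The text describes no practice walk of the 18-minute test; Figure 1 is not shown in the copy reviewed.

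The analysis (VIII. Statistical Analysis) has no period term: "the non-parametric Wilcoxon Signed Rank Sum test will be performed with significance interval of 0.05 on all applicable variables". The primary endpoint is walk distance and duration.

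The aim is comparative. The hypothesis in II. Overall Study Objective is that "HVNI therapy, when implemented in conjunction to ambulatory practices, will be more effective than TAU to improve patient mobility", and the same section says that the endpoints "will establish the effect HVNI therapy may have on improving patient ambulation relative to TAU". V. Subject Enrollment gives N=26 for 90% power at alpha 0.05, citing a mean difference of 42.93 m, with up to 32 enrolled. It also says that the data will be used to size a later randomised study.

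**The concern.** A crossover protects a treatment comparison from period effects because some subjects take the treatments in each order. Here there is one order. Anything that makes the second walk differ from the first is counted as HVNI effect: familiarity with the course and the test, fatigue, or a change in clinical state over an open-ended gap. The direction is unknown. A gain on the second walk can produce a significant result when HVNI does nothing, and a loss can hide a real benefit.

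Both primary measures and the within-subject secondary comparisons are affected, and nothing done after data collection can repair it. A constant order shift does not alter the SD of the paired differences, so that quantity can still inform the follow-on study. The observed mean difference cannot be used for sizing without carrying the order effect with it.

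**Working it through.** **1. What can be estimated.** Let τ be the HVNI effect and π the effect of walking second. Under the plan every subject contributes second walk − first walk = HVNI − TAU, with expectation τ + π. There is no contrast in which τ and π appear with different signs, so only the sum is estimable, at any N and with any test.

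**2. Inputs.** From V. Subject Enrollment: N=26, power 90%, alpha 0.05, difference 42.93 m. The SD of paired differences, the sidedness of the test and the order effect are not given. I assume two-sided testing, normally distributed differences and order effects of 10, 20 and 30 m.

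**3. The plan's N.** Without an SD, N=26 can be neither reproduced nor refuted, so I back-solved. For a two-sided paired t-test with n=26, 90% power needs a standardised difference of 0.662, so SD = 42.93 / 0.662 ≈ 64.9 m. Other readings of the same figures give 63.3 m (Wilcoxon, two-sided) to 74.8 m (paired normal, one-sided). I use 50, 64.9 and 80 m as a range.

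**4. False positives when τ = 0** (signed-rank test with exact critical value, n=26, 40,000 simulations per setting; paired t by noncentral t in brackets):

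| Second-walk gain | SD 50 m | SD 64.9 m | SD 80 m |
|---|---|---|---|
| 10 m | 16% (17%) | 11% (12%) | 9% (9%) |
| 20 m | 49% (50%) | 32% (33%) | 22% (23%) |
| 30 m | 82% (84%) | 60% (62%) | 43% (45%) |

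A larger sample makes this worse. At an SD of 65 m and a 20 m gain, the rate rises from 31% at n=26 to 38% at n=32.

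**5. Loss of power when τ = 42.93 m.** A 20 m loss on the second walk leaves an expected difference of 42.93 − 20 = 22.93 m. Signed-rank power falls from 98% / 89% / 73% to about 60% / 40% / 28% at SD 50 / 64.9 / 80 m.

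**6. Follow-on sizing.** Suppose 42.93 m is observed and 20 m of it is order effect. A paired study sized for 90% power on 42.93 m needs 17 / 27 / 39 subjects. Its power at the true 22.93 m is about 43% / 42% / 42%.

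**7. Randomised order, 13 per sequence.** Take each subject's second walk minus first walk. Its expectation is τ + π in the TAU-HVNI sequence and −τ + π in the HVNI-TAU sequence. Half the difference between the sequence means is τ, and π cancels. The variance is ¼(SD²/13 + SD²/13) = SD²/26, the same as for the planned paired mean. At SD 64.9 m the standard error is 64.9/√26 = 12.7 m. One degree of freedom is lost. A rank-sum test on these period differences had simulated type I error of 4–5% at period effects of 0, 20 and 30 m. Its power for 42.93 m was 98% / 87% / 70%, against 98% / 89% / 73% for the signed-rank test with no period effect.

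**8. Carry-over.** If HVNI improves a later TAU walk by L metres, the HVNI-TAU expectation becomes −τ + π + L and the estimate becomes τ − L/2. With L = 20 m, 42.93 m is estimated as 32.93 m, and power at SD 64.9 m falls from 87% to 65%.

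**The case against.** The fixed order and the absence of randomisation are openly stated, the study is labelled feasibility, and a randomised study is to follow. Some of the wording is hedged. That would be a sufficient answer if the plan only described what was seen. It does not, because it states a superiority hypothesis, claims 90% power and tests at 0.05.

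The size of the bias rests wholly on assumptions. This stands. A 5 m shift gives about 6–8% false positives over the SDs used here, and a 20 m shift with an SD of 150 m gives about 10%. Nothing in the documents shows that the back-solved SD applies to an 18-minute walk. Only distance has been quantified; for duration, the 18-minute cap would limit an order effect. The sizing harm arises only if the observed mean difference is used, which the plan does not say. These points limit the magnitude and leave the confounding untouched.

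The plan has features that may shrink an order effect: no vigorous exercise in the 2 hours before a walk, a recovery interval, and otherwise unchanged management. They do not separate it from HVNI.

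Randomising order also has a price. TAU-first keeps HVNI carry-over out of the control walk. The rule in Control Session, "The Control session is treatment as usual (TAU), without use of HVNI during any time of this study period", bars HVNI only within that session, so it would not prevent carry-over from an earlier HVNI session. A separation requirement would constrain scheduling that is now left to the site. Power at SD 64.9 m would be 87%, slightly below the 90% target. Randomised order would also leave the study unblinded. All of this stands, and it is why a second route is offered.

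**Conclusion.** The concern holds and must be fixed. That treatment and period are fully confounded follows from the stated design and needs no assumption. A significant difference in distance or duration could not be attributed to HVNI, and a null result could not be read as no benefit. How far the result would be off is unknown: the bias equals an order effect whose size and direction the documents do not give. The percentages above illustrate assumed shifts of 10 to 30 m and SDs of 50 to 80 m; smaller shifts or larger SDs do less harm. Keeping both the fixed order and the superiority claim is not defensible.

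**What to change.** **Preferred.** Randomise session order 1:1 (TAU-HVNI or HVNI-TAU) within the same N.

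- State how the sessions will be separated so that HVNI carry-over into a later TAU walk is negligible.
- Collect end-of-study data after whichever session comes second.
- Analyse distance and duration with a period-adjusted comparison, for example a rank-sum test of within-subject period differences between the two sequences. For duration, use an exact or permutation p-value, because the 18-minute cap can produce ties.

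The cost is a protocol amendment: an allocation list for up to 32 subjects, revised session-order text in IV and VI, the separation statement and the relocated end-of-study collection. No subjects or sessions are added. The power cost and the carry-over risk are those shown in steps 7 and 8.

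**If adequate separation cannot be assured.** Keep the fixed order and replace the word crossover with single-sequence before-after. Remove the claim that the comparison can show HVNI to be more effective than TAU. State that the estimate, including any use of it to size the follow-on study, contains any period effect. This costs only wording.
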